Abbreviated Title: Phase 1 IFN + monocytes

Version Date: 12/04/2025

Abbreviated Title: Phase 1 IFN + monocytes

NIH Protocol #: 17-C-0011

Version Date: 12/04/2025

NCT Number: NCT02948426

Title: Phase 1 Study of Intraperitoneal Infusion of Autologous Monocytes with SYLATRON® (Peginterferon alfa-2b) and ACTIMMUNE® (Interferon gamma-1b) in Women with Recurrent or Refractory Ovarian Cancer, Fallopian Tube Cancer or Primary Peritoneal Cancer

NCI Principal Investigator:

[name]., Ph.D.
Women's Malignancies Branch (WMB)
Center for Cancer Research (CCR)
National Cancer Institute (NCI)
National Institutes of Health (NIH)
[name]
[name]
[name]
[contact]
E-mail: [contact]

Drug Name:	Sylatron® (Peginterferon alfa-2b)	Actimmune® (Interferon gamma-1b)	Autologous monocytes
BB-IND Number:	17040	17040	17040
Sponsor:	Center for Cancer Research, NCI	Center for Cancer Research, NCI	Center for Cancer Research, NCI
Manufacturer:	Merck	Horizon Pharma, Inc.	Department of Transfusion Medicine (DTM)

Commercial Agents: None

PRÉCIS

Background:

- Monocytes can differentiate into classic M1 macrophages inhibiting tumor proliferation and promoting natural killer (NK) cell differentiation.
- Human alpha interferons (interferon alfa, IFN α), interferon gamma (IFN γ) and monocytes have strong anti-neoplastic response in vitro and in vivo
- IFN α and IFN γ have been shown in early phase clinical trials to be safely administered intraperitoneally.
- Intraperitoneal monocytes alone or activated with IFN γ are safe and feasible as demonstrated in phase I clinical studies.
- We have shown that the combination of human monocytes, IFN- α 2a and IFN- γ 1b, or pegylated IFN- α , act synergistically against tumor cells in vitro and in mouse models.

Objectives:

- To identify a maximum tolerated dose of intraperitoneal autologous monocytes and Sylatron® (Peginterferon alfa-2b) and Actimmune® (Interferon gamma-1b).

[figure not shown]
Eligibility:

- Advanced metastatic or unresectable epithelial ovarian cancer, primary peritoneal cancer or fallopian tube cancer that is relapsed and resistant or refractory to prior platinum-based standard care systemic regimen.
- Patients must be off prior chemotherapy, radiation therapy, hormonal therapy or biological therapy for at least 4 weeks.
- ECOG performance status 0-1 and adequate organ and marrow function.

Design:

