2 ELIGIBILITY ASSESSMENT AND ENROLLMENT

2.1 ELIGIBILITY CRITERIA

2.1.1 Inclusion Criteria

2.1.1.1 Patients must have histologically or cytologically confirmed advanced metastatic or unresectable epithelial ovarian cancer, primary peritoneal cancer or fallopian tube cancer that is relapsed and resistant (recurred less than 6 months after chemotherapy) or refractory (progressed on chemotherapy) to prior platinum- and taxane-based standard care systemic regimen. Or patients who are not eligible for additional platinum therapy. Histopathologic diagnosis must be confirmed in the Laboratory of Pathology (LP), NCI.

2.1.1.2 Patients must have measurable or evaluable disease. Measurable disease is defined as at least one lesion that can be accurately measured in at least one dimension (longest diameter to be recorded for non-nodal lesions and short axis for nodal lesions) as ≥ 20 mm with conventional techniques or as ≥ 10 mm with spiral CT scan. See Section 6.3 for the evaluation of measurable disease. Evaluable disease includes CA125, ascites, peritoneal carcinomatosis, as defined in Section 6.3.1.

- 2.1.1.3 Patients must be at least 4 weeks from previous therapy (chemotherapy, hormonal therapy, and radiation therapy, immunotherapy and monoclonal antibodies, alternative therapy or investigational therapeutic agents). There is no limitation on the amount of prior therapies allowed. Patients with ovarian cancer 4 weeks from previous therapy have been found to have normal monocyte function (unpublished).
- 2.1.1.4 Patients who have had cranial radiation therapy need to have completed it \geq 8 weeks prior to enrollment.
- 2.1.1.5 Patients are permitted to receive investigational imaging agents while on study.
- 2.1.1.6 Patients who have had major surgery must be fully recovered and require a recovery period of \geq 4 weeks prior to enrolling on study.
- 2.1.1.7 Age \geq 18 years. Because no dosing or adverse event data are currently available on the use of intraperitoneal monocytes, IFN α 2 or IFN γ in patients $<$ 18 years of age, children are excluded from this study, but will be eligible for future pediatric trials.
- 2.1.1.8 ECOG performance status \leq 1 (Karnofsky \geq 70%, see [Appendix A](#)).
- 2.1.1.9 Adequate renal function, defined as serum creatinine \leq 1.5 X upper limit of normal (ULN), or measured creatinine clearance \geq 60 mL/min/1.73m 2 .

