- 2.1.1.10 Adequate hepatic function, defined as AST and ALT levels \leq 3 X ULN and total bilirubin $<$ 1.5 X ULN, unless known diagnosis of Gilbert's syndrome, where bilirubin \leq 5 mg/dl will be permitted. Gilbert's syndrome will be defined as elevated unconjugated bilirubin, with conjugated (direct) bilirubin within the normal range and less than 20% of the total. Total bilirubin will be permitted up to 5 mg/dl, if patients have historical readings consistent with the definition of Gilbert's syndrome prior to entering study.
- 2.1.1.11 Adequate bone marrow function, defined as absolute neutrophil (ANC) \geq 1,500/mm 3 (\geq 1.5 X10 6 /L), platelet count \geq 75,000/mm 3 (\geq 75 X10 6 /L), and hemoglobin \geq 8 g/dL (transfusion to obtain hemoglobin \geq 8 g/dL is allowed).
- 2.1.1.12 The effects of intraperitoneal monocytes, IFN α 2, and IFN γ on the developing human fetus are unknown. For this reason and because interferons based on animal data may cause fetal harm, women of child-bearing potential (excludes women with recurrent ovarian cancer) and men must agree to use adequate contraception (hormonal or barrier method of birth control; abstinence) prior to study entry and for the duration of study participation. Should a woman become pregnant or suspect she is pregnant while she is participating in this study, she should inform her treating physician immediately.
- 2.1.1.13 Ability of subject to understand and the willingness to sign a written informed consent document.

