<http://dsm.psychiatryonline.org/doi/full/10.1176/appi.books.9780890425596.dsm04>) requiring medical treatment will not be eligible to enroll, based on the black box warning (SYLATRON™ (peginterferon alfa-2b) for injection, for subcutaneous use. Merck Sharp & Dohme Corp., a subsidiary of Merck & Co., Inc., Whitehouse Station, NJ). Exception to this is if patients experienced transient post-partum depression that resolved and patient has been off treatment for >10 years. Patients who are taking oral anti-depressants for normal sadness, bereavement, or grief will not be excluded.
- 2.1.2.10 Pregnant women are excluded from this study because interferons based on animal data may cause fetal harm. Because there is an unknown but potential risk for adverse events in nursing infants secondary to treatment of the mother with interferons, breastfeeding should be discontinued if the mother is treated with intraperitoneal interferons. These potential risks may also apply to other agents used in this study.

2.1.2.11 Patients on combination antiretroviral therapy for the treatment of HIV are ineligible because of the potential for pharmacokinetic interactions with interferons alfa and gamma.

2.1.2.12 Patients receiving any medications or substances that are potent inhibitors or inducers of CYP1A2 or CYP2D6 are ineligible. Lists including such medications and substances are provided in [Appendix C](#).

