Assessment of disease by imaging (may include CT chest, abdomen and pelvis)	Within 28 days prior to treatment
Ophthalmic evaluation including visual acuity and funduscopic examination performed by an ophthalmologist	Within 180 days (-14 days) prior to treatment
Assessment of venous access in Department of Transfusion Medicine	Anytime prior to apheresis
Intraperitoneal catheter placement in Interventional Radiology, if not already placed OR surgical implantation of intraperitoneal port by Gynecologic Oncology if not already placed OR verification by clinicians of functional IP catheter or IP port (if pre-existing)	X
CBC with differential and platelet count	X
Metabolic panel (magnesium, calcium, albumin, phosphorus)	X
Acute care panel (electrolytes, glucose, BUN, creatinine)	X

Assessment	Timeframe (calendar days)
	Within 7 days prior to treatment (unless otherwise noted)
Hepatic function tests (AST/ALT/total bilirubin)	X
CA125	X
β-HCG in women of childbearing potential	X

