8.6.1 Maternal exposure

If a patient becomes pregnant during the course of the study, the study treatment should be discontinued immediately and the pregnancy reported to the Sponsor no later than 24 hours of when the Investigator becomes aware of it. The Investigator should notify the Sponsor no later than 24 hours of when the outcome of the Pregnancy becomes known.

Pregnancy itself is not regarded as an SAE. However, congenital abnormalities or birth defects and spontaneous miscarriages that meet serious criteria (section [8.1.2](#)) should be reported as SAEs.

The outcome of all pregnancies should be followed up and documented.

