8.6.2 Paternal exposure

Not applicable to this trial, as men are not included in the patient population.

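### Criterion 2.1.1.12 exempts women with recurrent ovarian cancer from the contraception duty by diagnosis, and on a natural reading from the β-HCG test as well

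*Combined protocol and SAP*

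**What the plan says.** Criterion 2.1.1.12 opens with its reason: "The effects of intraperitoneal monocytes, IFN α 2, and IFN γ on the developing human fetus are unknown". It then states who must agree to contraception: "women of child-bearing potential (excludes women with recurrent ovarian cancer) and men must agree to use adequate contraception". It closes by telling any participating woman who becomes pregnant, or suspects it, to inform her physician.

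The trial title names "Women with Recurrent or Refractory Ovarian Cancer, Fallopian Tube Cancer or Primary Peritoneal Cancer". Criterion 2.1.1.1 admits "advanced metastatic or unresectable epithelial ovarian cancer, primary peritoneal cancer or fallopian tube cancer that is relapsed and resistant", and also admits refractory disease and patients who cannot have more platinum. Criterion 2.1.1.7 sets the minimum age at 18.

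Pregnancy is dealt with in four other places:

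- Exclusion 2.1.2.10: "Pregnant women are excluded from this study because interferons based on animal data may cause fetal harm".
- The screening table in 2.2.2 lists "β-HCG in women of childbearing potential", and the baseline table in 2.5 has the same row.
- Section 3.5.1 makes a positive pregnancy test a reason for removal from therapy.
- Section 8.6.1 sets out what follows "If a patient becomes pregnant during the course of the study". Section 8.6.2 declares paternal exposure not applicable because "men are not included in the patient population".

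**The concern.** A contraception criterion protects a possible fetus from a drug with unknown or suspected fetal effects. It therefore needs to turn on whether a woman could become pregnant. This one turns instead on tumour site and recurrence. For women with recurrent ovarian cancer, who are central to the trial, it answers the question in advance without looking at age, menopausal status or surgery.

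At stake is a premenopausal participant with recurrent ovarian cancer who still has reproductive potential. As written, she gives no contraception commitment. If staff read the β-HCG rows with the only delimitation that the protocol offers, she also has no pregnancy test before interferon is infused. The matter is participant and fetal safety. It does not touch the sample size, the power statement or the MTD analysis.

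**Working it through.** The plan gives no figure to reproduce. The check is to set the passages side by side, followed by one illustrative product.

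1. **Does eligibility make the exemption true?** The minimum age is 18 (2.1.1.7). Criterion 2.1.1.1 requires prior systemic therapy, not prior surgery, and admits unresectable disease. Criterion 2.1.1.6 applies only to patients who have had major surgery, so it does not presume surgery. Section 1.2.1 describes cytoreductive surgery as standard care, but that is background and not an entry condition. No criterion requires hysterectomy, oophorectomy or menopause. Infertility is therefore not guaranteed.

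2. **Who is exempt on the literal wording?** Women with recurrent ovarian cancer. Women with refractory ovarian cancer that never relapsed, and women with tubal or primary peritoneal cancer, are not. If ovarian cancer is meant collectively for the three sites, every relapsed participant is exempt. The documents give no split by site or by relapsed versus refractory status, so the share cannot be computed.

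3. **Does the exemption reach the test?** The tables in 2.2.2 and 2.5 limit β-HCG to women of childbearing potential and do not cite 2.1.1.12. The parenthesis in 2.1.1.12 is the only text in the documents that delimits that term. The labs row of the study calendar (3.4) points back to 2.2 and 2.5, so any limit there carries into on-study labs. This is a natural reading, but still an inference.

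4. **Does the rest of the protocol agree with the carve-out?** The fetal-harm reason in 2.1.1.12, exclusion 2.1.2.10, the removal criterion in 3.5.1 and the procedure in 8.6.1 all treat pregnancy in a participant as possible. The parenthesis treats it as impossible for a core group. The reference to men has no one to apply to under 8.6.2.

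5. **Size.** The documents give no rate of reproductive potential. Assume 1% to 5%. Section 3.1.3 says that escalation has concluded, and Section 2.4 plans 10 expansion patients. Expected number = patients × rate: 10 × 0.01 = 0.1 and 10 × 0.05 = 0.5. This takes all 10 as exempt and still to be enrolled. Accrual status is not given, so the product is an upper figure for that cohort at each assumed rate.

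**The case against.** The best defence is intent. Most candidates will have had standard surgery and platinum-taxane chemotherapy, and the authors probably took them to be infertile. That is plausible, and it points to loose drafting. It does not rescue the wording: a woman who is infertile would be outside the category by her own status, so the parenthesis changes the outcome only for a woman who is not.

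A second defence is that the later provisions are not in strict logical conflict. The exclusion of pregnant women is unconditional, and 3.5.1 and 8.6.1 work coherently for patients outside the carve-out. This stands in part. It is why the carve-out is said to sit badly with those sections and not to make them unworkable.

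A reader might infer more than the documents support in four ways:

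- *That most of the population is exempt and only a minority is covered.* No figure supports either word, and refractory, never-relapsed ovarian patients remain covered on the literal text.
- *That exempt women certainly skip β-HCG.* The tables could be read in the ordinary sense of the term, and the positive-test rule suggests that testing was still expected.
- *That the pregnancy exclusion then rests on self-report alone.* History, physical examination and disease imaging are also required before treatment. None is a designated pregnancy check, but they are not nothing.
- *That 0.4 to 2 women are affected.* This comes from 40 × 0.01 and 40 × 0.05. It applies the assumed rate to the whole accrual ceiling, although escalation is over and not every patient is exempt.

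**Conclusion.** The point holds in a limited form. Criterion 2.1.1.12 classifies childbearing potential by diagnosis, nothing in the eligibility criteria makes that classification safe, and no other section corrects it. The exemption from contraception is explicit for women with recurrent ovarian cancer. The exemption from β-HCG is a reasonable inference from a shared and otherwise undefined term.

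The exempted share is unknown. The expected number of women with real reproductive potential is probably well below one: 0.1 to 0.5 of the 10 expansion patients, on an assumed 1% to 5% that has no source in the documents. The case for acting rests on the seriousness of fetal exposure, the inconsistency and the trivial cost of repair, not on frequency. The change should be made, but it has no bearing on the statistical design.

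**What to change.** In 2.1.1.12, remove the diagnosis-based parenthesis and the words *and men*. Reconcile the criterion with 2.1.2.10, the β-HCG rows in 2.2.2 and 2.5, Section 3.5.1 and Section 8.6, so that the existing contraception agreement and pregnancy test depend on a participant's actual childbearing potential and not on her tumour diagnosis. How that potential is defined is for the sponsor to decide; what matters here is that one definition serves all of these sections.

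The cost is a short wording amendment and an occasional extra β-HCG test. The test is already in the screening and baseline panels, so no new procedure is added.

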2.1.2 Exclusion Criteria

- 2.1.2.1 Patients who are receiving any other investigational agents (with exception of imaging agents as indicated above in section [2.1.1.5](#)).
- 2.1.2.2 Patients cannot have previously been treated with interferons (e.g., for chronic active hepatitis).
- 2.1.2.3 Lack of recovery of prior adverse events to Grade \leq 1 severity (National Cancer Institute Common Terminology Criteria for Adverse Events [NCI CTCAE] v 4.03) (except alopecia) due to therapy administered prior to the initiation of study drug dosing. Stable

persistent grade 2 peripheral neuropathy may be allowed as determined on a case-by-case basis at the discretion of the Investigator as interferon has not been shown to cause or exacerbate peripheral neuropathy.

- 2.1.2.4 Patients with active infection will not be eligible, but may become eligible once infection has resolved and at least 7 days have elapsed after antibiotics use was completed.
- 2.1.2.5 Concomitant chronic (daily or almost daily for ≥ 1 month prior) use of steroids or non-steroidal anti-inflammatory drugs (NSAIDS).
- 2.1.2.6 Patients with a recent history (within last 5 years) of autoimmune disease or inflammatory diseases will be excluded, because interferons may worsen these conditions. Exceptions will be allowed for vitiligo and hypothyroidism that has been stable on thyroid replacement medications for >6 weeks.
- 2.1.2.7 Impaired cardiac function or clinically significant cardiac disease including the following:
 - New York Heart Association class III or IV congestive heart failure
 - Myocardial infarction within the last 12 months
 - Subjects known to have impaired LVEF according to institutional standards
- 2.1.2.8 History of allergic reactions attributed to compounds of chemical or biologic composition similar to interferons or other agents used in the study.
- 2.1.2.9 Uncontrolled intercurrent illness including, but not limited to, ongoing or active infection, symptomatic congestive heart failure, unstable angina pectoris, cardiac arrhythmia, or psychiatric illness/social situations within the last 12 months that would limit compliance with study requirements. Patients with history of neuropsychiatric disorders or Major Depressive Disorder (DSM 5 definition:
<http://dsm.psychiatryonline.org/doi/full/10.1176/appi.books.9780890425596.dsm04>) requiring medical treatment will not be eligible to enroll, based on the black box warning (SYLATRON™ (peginterferon alfa-2b) for injection, for subcutaneous use. Merck Sharp & Dohme Corp., a subsidiary of Merck & Co., Inc., Whitehouse Station, NJ). Exception to this is if patients experienced transient post-partum depression that resolved and patient has been off treatment for >10 years. Patients who are taking oral anti-depressants for normal sadness, bereavement, or grief will not be excluded.
- 2.1.2.10 Pregnant women are excluded from this study because interferons based on animal data may cause fetal harm. Because there is an unknown but potential risk for adverse events in nursing infants secondary to treatment of the mother with interferons, breastfeeding should be discontinued if the mother is treated with intraperitoneal interferons. These potential risks may also apply to other agents used in this study.

2.1.2.11 Patients on combination antiretroviral therapy for the treatment of HIV are ineligible because of the potential for pharmacokinetic interactions with interferons alfa and gamma.

2.1.2.12 Patients receiving any medications or substances that are potent inhibitors or inducers of CYP1A2 or CYP2D6 are ineligible. Lists including such medications and substances are provided in [Appendix C](#).

2.1.3 Recruitment Strategies

This protocol may be abstracted into a plain language announcement posted on NIH websites and on NIH social media platforms.

2.2 SCREENING EVALUATION

2.2.1 Screening activities performed prior to obtaining informed consent

Minimal risk pre-screening activities that may be performed before the subject has signed a consent for this study include the following:

- Email, written, in person or telephone communications with prospective subjects
- Review of existing medical records to include H&P, laboratory studies, etc.
- Review of existing MRI, x-ray, or CT images
- Review of existing photographs or videos
- Review of existing pathology specimens/reports from a specimen obtained for diagnostic purposes

A waiver of consent for these activities has been requested in section [12.6.1](#).

2.2.2 Screening activities performed after a consent for screening has been signed (Registration Part 1)

The following activities will be performed only after the subject has signed the consent for this study for screening. Assessments performed at outside facilities or on another NIH protocol within the timeframes below may also be used to determine eligibility once a patient has signed the consent. For baseline evaluations, please see section [2.5](#).

Screening Assessments – Part 1

The following screening activities to determine eligibility may be performed any time prior to Registration Part 2.

Medical history, including age, performance status, and dates of prior treatment regimens.

Confirmation of tumor histology in NCI Laboratory of Pathology

(Archival tumor samples will be requested; if unavailable, the subject may choose to undergo fresh biopsy)

Assessment of disease by physical exam and imaging

Screening Assessments – Part 1

The following screening activities to determine eligibility may be performed any time prior to Registration Part 2.

(may include CT chest, abdomen and pelvis or MRI; report from outside institution is acceptable).

Screening Assessments – Part 2

Once patient eligibility has been established according to the results of the Screening Assessments Part 1 above, the following Screening Part 2 activities will be performed to determine final patient eligibility prior to Registration Part 2. Scans and x-rays must be done within 28 days (- 7 days) prior to the initiation of study therapy. All other studies should be performed within 7 days prior to initiation of study therapy, unless otherwise specified.

Assessment	Timeframe (calendar days)
	Within 7 days prior to treatment (unless otherwise noted)
History and physical examination	X
Assessment of disease by imaging (may include CT chest, abdomen and pelvis)	Within 28 days prior to treatment
Ophthalmic evaluation including visual acuity and funduscopic examination performed by an ophthalmologist	Within 180 days (-14 days) prior to treatment
Assessment of venous access in Department of Transfusion Medicine	Anytime prior to apheresis
Intraperitoneal catheter placement in Interventional Radiology, if not already placed OR surgical implantation of intraperitoneal port by Gynecologic Oncology if not already placed OR verification by clinicians of functional IP catheter or IP port (if pre-existing)	X
CBC with differential and platelet count	X
Metabolic panel (magnesium, calcium, albumin, phosphorus)	X
Acute care panel (electrolytes, glucose, BUN, creatinine)	X

Assessment	Timeframe (calendar days)
	Within 7 days prior to treatment (unless otherwise noted)
Hepatic function tests (AST/ALT/total bilirubin)	X
CA125	X
β-HCG in women of childbearing potential	X

